4.6.2 CLINICAL TRIAL VISITS

Screening Visit

This will be the first clinical trial visit for all subjects. The investigator will provide potential study participants with complete information about all clinical trial procedures as well as conditions of subject's participation.

During the Screening Visit, the investigator will determine subject's eligibility for the inclusion in this clinical trial.

The Screening Visit may take place for up to 21 days prior to the investigational medicinal product infusion (Day 0) to allow sufficient time for a wash-out period for those subjects that have recently received any administration of a fibrinogen-containing product (eg. fibrinogen concentrates, cryoprecipitate, fresh frozen plasma).

Assessments and procedures planned to be conducted during the Screening Visit will be performed only in the following order to avoid unnecessary assessments or procedures:

1. Information to be given to potential clinical trial subjects:
 - Subjects will be informed of the nature, purpose and procedures of the study, with a description of the possible risks involved.

- Subjects will be informed of the voluntary nature of participation, and of the right to withdraw from the study at any time, without this implying any negative consequences for the subject.
- Subjects will receive a *Patient Information Sheet* to take at home and they will be given enough time to think about their clinical trial participation.
- Investigator will make sure that potential subjects fully understand the elements of the *Patient Information Sheet*.

2. Clinical Trial Informed Consent:

Before any study-specific screening procedures will be performed, and after completely understanding the nature of the clinical trial, potential subjects or their parents or legal guardian for those subjects not qualified to give legal consent, must sign and date a *Clinical Trial Informed Consent*. The investigator will also sign and date it, thus reflecting that *Clinical Trial Informed Consent* has been obtained, and that the subject has had the opportunity to ask questions, and has received adequate answers. The subject will receive a signed copy of the informed consent form (ICF) and the original will be filed along with the study documentation.

3. Health Information Portability and Accountability Act (HIPAA)

The subject will be asked to sign HIPAA Authorization Form where necessary (Note: The HIPAA authorization may be included with the ICF).

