6. Assessment of concomitant medication: All concomitant medications, other than the investigational product, administered to the subject will be recorded.

The use of any concomitant medications during the PK study (between 1 week before the infusion and Day 14 post-infusion) should be avoided as much as possible. If clinical reasons make necessary the use of concomitant drugs, the treating physician will evaluate each case.

7. Review of inclusion and exclusion criteria to confirm subject eligibility (see [Sections 5.1 and 5.2](#)).

Subjects who do not fulfill all inclusion criteria (including laboratory criteria to be verified on Day 0 prior to the infusion) and/or fulfill any exclusion criteria (including laboratory criteria to be verified on Day 0 prior to the infusion) will be considered screening failures.

Only subjects who fulfill all inclusion criteria (including laboratory criteria to be verified on Day 0 prior to the infusion) and do not meet any exclusion criteria (including laboratory criteria to be verified on Day 0 prior to the infusion) will be considered eligible to continue with the following procedures of the study.

Infusion Visit (Day 0) - Infusion

After verification of compliance with all applicable Inclusion/Exclusion criteria, study staff may proceed with infusion of the investigational medicinal product according to the [Section 4.5.4.2 Dispensation and administration of the investigational product](#).

If the subject had a bleeding requiring replacement therapy with any fibrinogen-containing product between Screening Visit and investigational medicinal product infusion then, the investigational medicinal product infusion should not be carried out and the 21-day washout period be observed, thus postponing investigational medicinal product infusion (Day 0 Visit) as appropriate. In this case, screening/baseline (pre-infusion) samples should be taken again, and laboratory inclusion/exclusion criteria verified with the results of the most recent sample.

Briefly, a 70 mg/kg body weight single-dose of FIB Grifols will be intravenously administered at a rate that must not exceed 5 mL/minute. Study staff should make sure that the product is at room temperature before being administered. The exact volume infused to the subject will be recorded in subject's source documents and CRF/eCRF. The exact date and time of start and completion of the infusion will be also recorded.

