5. SELECTION AND WITHDRAWAL OF SUBJECTS

5.1 SUBJECT INCLUSION CRITERIA

Subject eligibility will be based on the presence of congenital fibrinogen deficiency manifested as afibrinogenemia and the willingness to participate the study.

Subjects fulfilling the following inclusion criteria are eligible for participation in the study:

1. Male or female subjects less than 70 years old^a.
2. Sign the written ICF, or the subject's parent or legal guardian signs the ICF where applicable, and the Subject Authorization Form (SAF) where applicable. Pediatric subjects, as defined by local regulations, will be asked to sign an age appropriate assent form.
3. Subjects diagnosed with congenital fibrinogen deficiency manifested as afibrinogenemia.
4. Subjects with a fibrinogen level undetectable¹, or equal or less than 30 mg/dL determined by both Clauss and antigen methods at baseline² (sample drawn within 24 hours prior to infusion on Day 0 Visit will be tested locally) or at Screening Visit³ (sample should be drawn at least 14 days prior to infusion on Day 0 Visit to be tested at central laboratory).

¹ Limit of detection for fibrinogen level determination must be 30 mg/dL or lower for both methods.

² For sites that have the capability of performing fibrinogen level determinations locally by both Clauss and antigen methods with a limit of detection of 30 mg/dL or lower.

³ For sites that do not have the capability of performing fibrinogen level determinations by both Clauss and antigen methods locally or have methods that are not sensitive enough (limit of detection: 30 mg/dL).

5. Female subjects of child-bearing potential^b must have a negative test for pregnancy blood or urine HCG-based assay at baseline (sample drawn within 24 hours prior to infusion on Day 0 Visit)
6. Female subjects of child-bearing potential^b and their partner have agreed to practice contraception using a method of proven reliability (ie, hormonal methods, barrier methods, intrauterine devices methods) to prevent a pregnancy during the course of the clinical trial
7. Subjects must be willing to comply with all aspects of the clinical trial protocol, including blood sampling, for the whole duration of the study

^aThe enrollment of pediatric subjects (below 18 years of age) will be initiated only after the safety of FIB Grifols in the adult subjects has been evaluated by the sponsor.

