#### **4.1.1.2 Plasma Concentration Values Below the Quantification Limit**

If any plasma concentration values of fibrinogen are below the lower limit of quantification (LLOQ) for either the activity (Clauss) method or the antigen (ELISA) method, in general the values will be replaced with a value of zero for the PK analysis. If necessary, alternative methods may be used to impute the values below LLOQ based on PK principle, and such methods will be documented in the CSR.

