## 9.2 Calculation of PK parameters

The PK parameters of plasma fibrinogen following single-dose administration in individual subjects will be determined as appropriate and as data permit. The PK parameters will include IVR, AUC calculated as  $AUC_{0-14\text{days}}$ ,  $AUC_{0-\infty}$ ,  $C_{\text{max}}$ ,  $t_{\text{max}}$ ,  $t_{1/2}$ , MRT, Vd, and Cl.

The PK parameters will be calculated using non-compartmental methods with WinNonlin software.

All PK parameters will be calculated using the fibrinogen concentration values obtained by both Clauss method and antigen (ELISA) method.

The pharmacokinetic parameters of interest will be determined as follows:

IVR	incremental in vivo recovery, calculated as $([FIB \text{ max (mg/dL)}] - [FIB \text{ pre-infusion (mg/dL)}]) / FIB \text{ administered (mg) / Body weight (kg)}$ , where the FIB max is the peak FIB activity during the first four hours of sampling after the end of infusion and FIB pre-infusion is the baseline FIB activity of the subject, expressed as mg/dL per
-----	---

	mg/kg. FIB administered will be the actual administered dose calculated using the actual volume administered to the subject, the potency, and the true concentration of FIB in the batch used.
AUC 0-14days	area under the concentration vs. time curve from time 0 to 14 days, calculated by a combination of linear and logarithmic trapezoidal methods and expressed in the unit of concentration × time (e.g., mg × h/dL). The linear trapezoidal method will be used for all incremental trapezoids arising from increasing concentrations and the logarithmic trapezoidal method will be used for those arising from decreasing concentrations.
AUC 0-∞*	area under the concentration vs. time curve from time 0 extrapolated to infinite time, calculated as AUC 0-t + C t /K el , where AUC 0-t is the area under the concentration vs. time curve from time 0 to the time of last quantifiable concentration (C t ), and K el is the apparent terminal first-order elimination rate constant, determined by linear regression analysis of the natural log-linear segment of the plasma concentration-time curve, expressed in time  units (1/h). At least 3 time points will be included in the determination of K el .

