C max	the first observed peak plasma fibrinogen concentration following the end of drug infusion obtained directly from the experimental data without interpolation, expressed in concentration units (mg/dL).
t max	the observed time to reach peak plasma fibrinogen concentration obtained directly from the experimental data without interpolation, expressed in time units (hour).
t ½*	the terminal half-life, calculated as ln(2)/K el , expressed in time units (hour).
MRT*	mean residence time, calculated as AUMC 0-∞ /AUC 0-∞ -(TI/2), expressed in time units (hour), where AUMC 0-∞ is the area under the first moment of the concentration vs. time curve from time 0 extrapolated to infinite time, and TI is the length of infusion.*
Cl*	clearance, calculated as Dose/AUC 0-∞ , expressed in units dL/h/kg.
Vd*	volume of distribution, calculated as Cl × MRT, expressed in units dL/kg.

\*Parameters relying on the determination of the apparent terminal first-order elimination rate constant (Kel) will not be reported if R^2<0.8 or the extrapolated AUC to infinity is >20%.

Considering different potencies from different lots are administered, the actual dose amount (mg/kg) infused may deviate from the planned or target dose of 70 mg/kg. All appropriate PK parameters, such as AUC and Cmax, will be dose normalized to 70 mg/kg body weight after taking into account the actual potency. In addition, PK parameters corrected for the baseline fibrinogen level of the subject will be calculated for all the PK parameters above. The correction will be based on the fibrinogen concentration measured pre-infusion. The calculations will be the same as those described above for the un-corrected PK parameters, except the fibrinogen concentration measured pre-infusion will be deducted from the concentrations of each post-infusion sample before the calculations.

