## **12 CHANGES IN PLANNED ANALYSIS IN PROTOCOL**

The evaluation of at least 90% of the planned dose was administered for the PP population will use the prepared volume per the pharmacy manual as the reference. The reason is that different potencies from different lots are administered, the actual dose in mg/kg body weight may deviate from the planned or target dose of 70 mg/kg automatically.

Incremental IVR will be calculated for fibrinogen levels from the peak level recorded within and including the first four hours after the end of infusion and reported as [mg/dL]/[mg/kg], not just the first hour. Based on preliminary data review of the fibrinogen levels, it seems that

$C_{max}$  occurs between 1 and 2 hours after the end of infusion, later than the previously planned 1 hour. So in order to ensure the  $C_{max}$  was captured the time duration is extended. Also, for RiaSTAP™, a fibrinogen concentrate (human), the incremental IVR was determined from fibrinogen levels obtained up to 4 hours post-infusion and we want to match that.

PK parameters corrected for the baseline fibrinogen level of the subject will be calculated, in addition to the uncorrected PK parameters as planned.

All appropriate PK parameters, such as AUC and  $C_{max}$ , will be dose normalized to 70 mg/kg body weight after taking into account the actual potency.

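### Does deducting one fixed baseline in SAP 9.2 spoil the corrected PK parameters when the baseline is earlier product still declining?

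*SAP*

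**What the plan says.** SAP 9.2 calculates every PK parameter twice: from the measured concentrations, and again after a correction in which "the fibrinogen concentration measured pre-infusion will be deducted from the concentrations of each post-infusion sample before the calculations". SAP 12 presents this as an addition: "PK parameters corrected for the baseline fibrinogen level of the subject will be calculated, in addition to the uncorrected PK parameters as planned". The rule does not ask where the baseline came from.

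Two places in Protocol 4.6.2 foresee subjects with earlier product. The screening window exists "to allow sufficient time for a wash-out period for those subjects that have recently received any administration of a fibrinogen-containing product". After a bleed treated with such a product before Day 0, "the investigational medicinal product infusion should not be carried out and the 21-day washout period be observed". Exclusion criterion 1 in Protocol 5.2 bars product within 21 days of Day 0. Protocol 2.7 cites a terminal half-life of 3.0 to 5.3 days.

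SAP 4.1.1.2 says of concentrations below the quantification limit that "in general the values will be replaced with a value of zero for the PK analysis". The documents give no central-laboratory limit. The nearest figure is the eligibility requirement in Protocol 5.1: "Limit of detection for fibrinogen level determination must be 30 mg/dL or lower for both methods".

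On the terminal fit, SAP 9.2 says "At least 3 time points will be included in the determination of" Kel. It withholds Kel-based parameters if R² is below 0.8 or the extrapolated AUC exceeds 20%.

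**The concern.** Twenty-one days is 21/5.3 = 4.0 to 21/3.0 = 7.0 half-lives, so a subject can reach Day 0 with some earlier product still circulating. It continues to fall during the 14 days of sampling, but the full baseline is taken off every sample. The over-deduction is largest in the late, low samples that determine Kel. Corrected half-life, AUC, MRT and Vd then come out too low and clearance too high.

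The sample size rests on PK, and SAP 9.3 summarises the parameters without separating subjects by the source of their baseline. A reader might take the corrected value for the better one when, in these subjects, it is the worse.

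**Working it through.** The plan gives no figure for residual product or for the size of the correction, so there is nothing to reproduce first.

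**Inputs.** From the documents: half-life h = 3.0 to 5.3 days (Protocol 2.7), with 4.0 added as a middle value; a gap of 21 days (Protocol 5.2); the adult sampling times to 336 h (Protocol 4.1); linear-up/log-down AUC and at least 3 terminal points (SAP 9.2). Assumed: one earlier dose with the same peak P as the study dose, the same half-life for both products, a noise-free one-compartment curve treated as a bolus, and P = 100 mg/dL where a level is needed. The percentages depend on the ratio of the two peaks, not on P.

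**Step 1, the leftover.** b = P × 2^(−21/h) = 0.8, 2.6 and 6.4 mg/dL for h = 3.0, 4.0 and 5.3 days.

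**Step 2, the corrected curve.** With k = ln 2/h, the measured level is (P + b)e^(−kt). After the deduction it is P·e^(−kt) − b(1 − e^(−kt)), so the error at time t is b(1 − e^(−kt)). At Day 14 it is 84% (h = 5.3) to 96% (h = 3.0) of b. At 4 h it is only 2 to 4% of b, so IVR and Cmax hardly move.

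**Step 3, one case by hand (h = 5.3).**
- Day 6: 45.6 − 6.42 × 0.544 = 42.1
- Day 9: 30.8 − 6.42 × 0.692 = 26.4
- Day 14: 16.0 − 6.42 × 0.840 = 10.6

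The log-linear slope through these points is about −0.173 per day, which gives a half-life of about 4.0 days instead of 5.3.

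**Step 4, all cases (21-day gap, last 3 points).**

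| True half-life (days) | 3.0 | 4.0 | 5.3 |
|---|---|---|---|
| Corrected half-life (days) | 2.72 | 3.34 | 4.01 |
| Error in half-life | −9.5% | −16.5% | −24.4% |
| Error in AUC0-∞ | −3.0% | −7.7% | −14.6% |
| Error in Cl | +3.1% | +8.3% | +17.1% |
| Error in MRT | −5.7% | −12.3% | −20.6% |
| Extrapolated AUC | 3.0% | 5.8% | 9.4% |
| Uncorrected half-life error | 0 | 0 | 0 |
| Uncorrected AUC0-∞ error | +0.8% | +2.6% | +6.4% |

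R² is above 0.998 throughout, so both filters pass. With 5 terminal points the half-life errors are −6.9, −12.8 and −19.9%.

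**Step 5, sensitivity of the half-life error (last 3 points).**
- Earlier dose half as large: −5, −8, −12%.
- Gap of 28 days: −2, −5, −10%.
- Gap of 35 days: 0, −2, −4%.
- Baseline below the quantification limit and set to zero: no effect.

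**Step 6, effect on the summary.** One affected subject in 10 moves the mean corrected half-life by a tenth of the individual error: 0.7% (5 points, 3.0 days) to 2.4% (3 points, 5.3 days).

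**Step 7, the obvious alternative.** Deducting b·e^(−kt), with k taken from the subject's uncorrected profile, restores the true curve when the baseline is residual product. The trigger would have to be a recorded earlier product plus a measurable baseline, and that cannot tell residual product from own fibrinogen, which Protocol 5.1 admits up to 30 mg/dL. Misapplied to own fibrinogen at P = 100 (last 3 points):
- Own 10 mg/dL, h = 3.0: half-life 6.13 days (+104%), AUC0-∞ +37%.
- Own 8 mg/dL, h = 4.0: half-life 5.91 days (+48%), AUC0-∞ +24%.

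In both, extrapolation is about 18% and R² at least 0.98, so the wrong values would be reported. The constant deduction has no error in either case.

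**The case for a change.** The best argument for a change is that the rule is wrong in a situation the protocol itself describes, that the error has a known direction, and that the filters miss it. The quantification limit is not stated, and 30 mg/dL is only an upper bound on the detection limit required for eligibility, so one cannot assume that every residual is set to zero. If every baseline were zeroed, the corrected set would equal the uncorrected one. The set matters only when a baseline is measurable, and then its source matters too. Prior blood-derived products are recorded for 3 months (Protocol 4.6.2), so a rule that depends on them needs no new data.

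All of this stands as a description of the bias. It does not make the replacement better. In the flagged subjects a decaying deduction returns the same half-life and MRT as the uncorrected set, so for those parameters it adds nothing. For AUC it removes an uncorrected error of 1 to 6%. Against that, it puts much larger errors into subjects with own fibrinogen who happen to have received product recently. How many subjects are of each kind is unknown, and a single baseline value does not reveal it.

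**Conclusion.** The over-correction is real but narrow, and the constant deduction can stay. It requires a baseline above an unstated quantification limit, made up of earlier product, from a dose close to the 21-day boundary. A dose exactly 21 days before is arguably already excluded. At worst, among single equal earlier doses, it shortens one subject's corrected half-life by 24%. At a 28-day gap the figure is 2 to 10%, and it is zero if the baseline is below the limit.

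It touches only a supplementary set. No PK hypothesis is tested, the parameters planned in Protocol 9.1.2 remain in uncorrected form, and their half-life is exact in this situation. An analyst who sees corrected and uncorrected half-lives diverge can find the reason in material already planned: baseline concentrations by subject (SAP 9.1) and medication dates (SAP 8.1) are listed. SAP 4.2 allows unreliable profiles to be excluded with a flag, and SAP 1 allows further analyses documented in the study report.

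These sizes rest on the assumed equal peaks, equal half-lives, noise-free curves and the adult schedule. A fixed, transparent deduction that is exact for own fibrinogen, shown beside the uncorrected results, is a reasonable choice.

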### 9.3 Descriptive Statistics of PK Parameters

Descriptive statistics (summarized separately for adult and pediatric populations, including n, mean, SD, 90% CI for mean, %CV, median, minimum, and maximum will be calculated for all PK parameters. Geometric mean and 90% CI for geometric mean will also be calculated for all PK parameters (except  $t_{max}$ ). If data allow, PK parameters for the pediatric population will also be summarized by age group as appropriate (e.g. <2,  $\geq 2$  - <12,  $\geq 12$  - <18 years).

## 10 EFFICACY ANALYSIS

Efficacy analyses will be performed on the Evaluable population. As sensitivity analyses, the efficacy analyses will also be assessed on the PP population (if different from the Evaluable population).

All analyses on efficacy parameters (including the primary, secondary, [REDACTED] efficacy endpoints) will be carried out in the overall study population (adult subjects plus pediatric subjects), and will also be conducted in the adult population and the pediatric population separately. The primary efficacy analyses will be the ones performed on the overall study population.

All efficacy variables and their changes from baseline (pre-infusion) will be summarized descriptively by planned day and time. Other than number of non-missing values, mean, SD, median, minimum and maximum, 25th percentile (Q1) and 75th percentile (Q3) will also be calculated. Summary tables and figures will be provided.

### 10.1 Primary Efficacy Analysis

The primary efficacy endpoint is the mean change (difference) on the MCF variable measured on pre-infusion and 1-hour post-infusion plasma samples by ROTEM in the Evaluable population.

For the primary efficacy endpoint, the change (difference) between the pre-infusion and 1-hour post-infusion MCF, the statistical null hypothesis ( $H_0: \Delta = 0$ ) of no difference will be tested against two-sided alternative hypothesis ( $H_1: \Delta \neq 0$ ) with a one sample t-test for paired observations. The maximum permitted type 1 error will be 5%, two-sided.

The same analysis will be performed using the median value by the Wilcoxon signed rank test. In addition to this, the two analyses above will be performed using the PP population.

[REDACTED]

### 10.2 Secondary Efficacy Analyses

Secondary efficacy analyses will be performed in the Evaluable and PP populations. Secondary efficacy variables including change (difference) in other thromboelastographic variables (CT, CFT,  $\alpha$ ) and standard coagulation tests (TT, PT, aPTT) in plasma samples pre-

infusion and 1-hour post-infusion will be summarized by adult and pediatric populations and overall.

Statistical analyses using the one sample t-test for paired observations and the Wilcoxon signed rank test will be performed on the secondary efficacy endpoints, similar to the analyses on the primary efficacy endpoint.

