4.6.1.8 Standard coagulation tests

Following standard coagulation tests: TT, PT, and aPTT will be performed on frozen plasma samples at the central laboratory of the study.

Samples for standard coagulation tests will be taken at:

1. Infusion Visit (Day 0):
 - iii. Immediately prior (within 60 minutes prior) to the scheduled infusion
 - iv. At 30 minutes (not applicable for pediatric subjects), 1 hour, and 4 hours (not applicable for pediatric subjects) after completion of the infusion
2. Day 1 (24 hours post-infusion, not applicable for pediatric subjects)
3. Day 2 (48 hours post-infusion, not applicable for pediatric subjects)
4. Day 4 (96 hours post-infusion, not applicable for pediatric subjects)
5. Day 6 (144 hours post-infusion, not applicable for pediatric subjects)
6. Day 9 (216 hours post-infusion, not applicable for pediatric subjects)

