9.5 PROCEDURES FOR ACCOUNTING FOR MISSING, UNUSED, AND SPURIOUS DATA

For the PK analysis, any missing or not valid values for fibrinogen concentration will be treated as missing, or if necessary, will be interpolated or extrapolated using PK principle, as appropriate, and will be documented in the clinical study report.

For primary efficacy endpoint analysis, the missing value in change from baseline in MCF will be set to zero.

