9.7.2 POPULATION FOR STATISTICAL ANALYSIS OF EFFICACY

Two study populations for statistical analysis of efficacy will be used: evaluable population and PP population. All efficacy analysis will be primarily run on the evaluable population and then they will be also run on PP.

Definition of evaluable population:

The evaluable population will include all subjects who received investigational product at any amount and who have at least two measurements for the primary efficacy variable: one pre-infusion MCF and 1-hour post-infusion MCF measurements by ROTEM.

Definition of PP:

The PP population will include all subjects who received planned dose of the investigational product (at least 90% of the planned dose), who have no major protocol violation (to be defined in a data review meeting prior to database lock), and who have at least two measurements for the primary efficacy variable: one baseline (pre-infusion) MCF measurement by ROTEM and 1-hour post-infusion MCF measurement by ROTEM for the investigational medicinal product.

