### **Evaluable population (efficacy)**

The Evaluable population will include all subjects who received IP at any amount and who have at least two measurements for the primary efficacy variable: one pre-infusion MCF and 1-hour post-infusion MCF measurements by ROTEM.

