### **Per-protocol population (efficacy)**

The Per-protocol (PP) population will include all subjects who received planned dose of the IP (at least 90% of the planned dose based on the prepared volume), who have no major protocol violation that might have impact on the primary efficacy assessment (to be defined in a data review meeting prior to database lock), and who have at least two measurements for the primary efficacy variable: one baseline (pre-infusion) MCF measurement by ROTEM and 1-hour post-infusion MCF measurement by ROTEM for the investigational medicinal product.

Any deviations from the protocol will be recorded in the protocol deviation list. The validity of a subject for inclusion in each of these four populations (Safety, PK, Evaluable, and PP) will be assessed at a data review meeting that will take place before database lock. The data review meeting will review the protocol deviation list, as well as data listings. If additional protocol deviations are identified which justify removing a subject from any population, then these decisions will be documented.

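### Both efficacy populations require a pre-infusion and a 1-hour MCF, so a subject with either one missing is left out of the TT, PT and aPTT analyses even when those results are complete

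*SAP*

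**What the plan says.** SAP section 10 opens with a general rule, "Efficacy analyses will be performed on the Evaluable population", and adds the per-protocol (PP) set as a sensitivity analysis. The same section says: "All efficacy variables and their changes from baseline (pre-infusion) will be summarized descriptively by planned day and time". Section 10.2 repeats the population rule for the secondary endpoints, "Secondary efficacy analyses will be performed in the Evaluable and PP populations". These endpoints are CT, CFT and alpha angle from ROTEM, and the coagulation tests TT, PT and aPTT.

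SAP section 4.2 limits the Evaluable population to subjects who received any amount of product and "who have at least two measurements for the primary efficacy variable: one pre-infusion MCF and 1-hour post-infusion MCF measurements by ROTEM". The PP set adds criteria on dose and major violations. It keeps the MCF requirement: subjects "who have at least two measurements for the primary efficacy variable: one baseline (pre-infusion) MCF measurement by ROTEM", together with a 1-hour value.

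The protocol has the same rule. Section 9.7.2 says "All efficacy analysis will be primarily run on the evaluable population and then they will be also run on PP", and section 9.1.3.2 places the secondary variables on the same two sets.

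The coagulation tests have their own procedure, protocol section 4.6.1.8: "TT, PT, and aPTT will be performed on frozen plasma samples at the central laboratory of the study". ROTEM is described separately in section 4.6.1.7, with the same sampling times.

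On missing data, SAP section 4.1 imputes nothing unless otherwise noted. SAP section 4.1.2 sets an undetectable MCF or alpha angle to 0 and an undetectable CT or CFT to missing. Protocol section 9.5 says "the missing value in change from baseline in MCF will be set to zero", for the primary endpoint analysis only.

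**The concern.** A requirement for both MCF values suits the MCF analysis. For the other endpoints it makes inclusion depend on a measurement that they do not use. A subject can have complete pre-infusion and 1-hour TT, PT and aPTT and still be absent from those analyses because a different assay gave no result. The PP analysis cannot bring the subject back, because it carries the same condition. The visible text defines no full-analysis or endpoint-specific set.

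Adults have ROTEM and coagulation samples up to Day 9, so an adult excluded for one MCF also leaves the summaries at 30 minutes, 4 hours and Days 1 to 9. At stake is precision in a trial that plans about 10 evaluable subjects per age group in a rare disease and does not replace subjects who discontinue after dosing (protocol section 5.3).

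**Working it through.** **The plan's own figure.** SAP section 4.3 enrols 11 per age group to obtain 10 evaluable, and for children it states 10% dropout. 10 × 1.10 = 11 reproduces this; 10 / 0.90 = 11.1 would round up to 12. No effect size, SD or power is given for any efficacy endpoint, so only precision can be examined.

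**Who is excluded.**

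- MCF missing or invalid before infusion or at 1 hour, with no valid re-run: excluded from both efficacy sets.
- MCF undetectable at either time: set to 0 under SAP section 4.1.2, so the subject stays in.
- ROTEM failure at any other time: nobody is excluded.

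**What one exclusion removes.** There are 7 efficacy variables, 4 from ROTEM and 3 coagulation tests. Adults are sampled at 9 times (pre-infusion, 30 minutes, 1 hour, 4 hours, Days 1, 2, 4, 6 and 9) and children at 2 (pre-infusion and 1 hour). The counts are scheduled values; undetectable CT or CFT would lower them.

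| | Adult | Child |
|---|---|---|
| Scheduled values | 9 × 7 = 63 | 2 × 7 = 14 |
| Lost with the failed run | 4 | 4 |
| Coagulation values removed by the rule | 9 × 3 = 27 | 2 × 3 = 6 |
| Other ROTEM values removed by the rule | 8 × 4 = 32 | 1 × 4 = 4 |
| Total removed by the rule | 59 | 10 |

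For the paired 1-hour tests, the avoidable loss is three pairs per subject: TT, PT and aPTT. If the whole run failed, the CT, CFT and alpha pairs are gone under any rule.

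**Effect on precision.** The 95% CI half-width for a mean change, in SD units, is t(0.975, n−1)/√n.

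| n | Half-width | Change |
|---|---|---|
| 10 | 0.715 | reference |
| 9 | 0.769 | +7.5% |
| 8 | 0.836 | +16.9% |
| 20 | 0.468 | reference |
| 19 | 0.482 | +3.0% |
| 18 | 0.497 | +6.3% |

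**How often.** The documents give no failure rate. Assume an independent probability f, per required measurement, that MCF is unavailable and cannot be re-run. A subject is then excluded with probability q = 1 − (1 − f)². Among 22 enrolled, the expected number is 22q and the chance of at least one is 1 − (1 − q)²².

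| f (assumed) | q | Expected among 22 | Chance of at least one |
|---|---|---|---|
| 1% | 0.0199 | 0.44 | 0.36 |
| 2% | 0.0396 | 0.87 | 0.59 |
| 5% | 0.0975 | 2.1 | 0.90 |

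These rates overstate the avoidable loss wherever the coagulation sample is missing as well.

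**The case against.** The strongest reply is that one common efficacy set is simple, keeps n equal across endpoints, and is what the protocol prescribes. ROTEM and coagulation samples share sampling times, frozen plasma and the central laboratory, so a missed draw or lost shipment would probably remove both. The narrower case of ROTEM-only loss may be rescued from retention plasma, which protocol section 4.6.1.16 keeps for purposes that include repeat testing. Adults have pre-infusion and 1-hour retention samples; children have the pre-infusion one only. Enrolment of 11 leaves 10 after one loss, and the visible SAP plans no confidence interval for efficacy. All this stands and limits the size of the problem. It does not give a reason to drop complete coagulation pairs, and a possible re-run is not an analysis rule.

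Some text is also out of view. The protocol contents list sections on change over time that do not appear in the body, and text after SAP section 10.1 is redacted. A specific rule for time courses could be there. The general opening of SAP section 10 and protocol section 9.7.2 are visible and unqualified.

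A reader might infer more than the documents support:

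- **Any failed ROTEM run excludes the subject.** Only the pre-infusion and 1-hour runs count.
- **The data are thrown away.** SAP section 4 still lists them, and the PK and safety populations do not depend on MCF.
- **The coagulation results would be biased towards subjects in whom ROTEM worked.** No mechanism links a technical ROTEM failure to TT, PT or aPTT, and a plasma with no measurable clot is kept with MCF 0.
- **The protocol expects missing MCF.** Section 9.5 gives a handling rule for the primary endpoint, not a forecast.

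**Conclusion.** The point holds, with modest consequences. As written, a missing or invalid MCF at either of two times removes a dosed subject from analyses that do not need MCF, and no visible rule restores the subject. If nobody is affected, no result changes. With one subject affected, the loss is about 7.5% in CI half-width within an age group and 3% overall; with two in the same age group, about 17% there.

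These figures assume 10 subjects per age group with otherwise complete data, and one or two subjects who lose only ROTEM; the documents supply neither a count nor a rate. If all 11 in a group are dosed and complete, one loss takes n from 11 to 10 and the half-width from 0.672 to 0.715, about 6%. The 59 of 63 values for an adult should not be read as typical or as independent information: they are correlated repeats from one subject, and a child has 10 such values. The primary MCF analysis is not at issue here.

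**What to change.** - Keep the MCF-based Evaluable population for the primary MCF analysis.
- In SAP sections 10 and 10.2, analyse the 1-hour change of each secondary variable in all dosed subjects with a pre-infusion and a 1-hour value of that variable.
- For PP analyses of secondary variables, replace the MCF pair by the pair of the variable concerned, and keep the dose and violation criteria.
- Summarise observed values over time in all dosed subjects with a value at that time point. Require a baseline value only for change-from-baseline summaries. A baseline requirement throughout would remove valid post-infusion CT and CFT from any subject with no measurable clot at baseline, because undetectable CT and CFT are set to missing.
- Print n for every variable and time point.
- Record the departure from protocol sections 9.1.3.2 and 9.7.2 in SAP section 12.

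The cost is small, but a reader might take it for a change of SAP wording alone. The protocol states the same rule, so a documented change from the protocol is needed. n can then differ between endpoints; the SAP already plans to report the number of non-missing values, so this adds little work.
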